## **6.6 Study timetable and end of study**

The study is expected to start on November 2008 and to be completed by December 2012. Anticipated duration of the trial (recruitment of all patients to last patient last visit) is 49 months.

The study may be terminated at individual centres if the study procedures are not being performed according to GCP, or if recruitment is slow. AstraZeneca may also terminate the

entire study prematurely if concerns for safety arise within this study or in any other study with AZD2281.

**Table 11 Study timetable**

Activity / Milestone	Approximate Timings
FPI	[REDACTED]
LSI	[REDACTED]
Data Cut-off	[REDACTED]
Final LSLV	[REDACTED]
End of Study	[REDACTED]

The end of this study is defined as the date of the last visit of the last patient, occurring when all patients have completed study therapy.

If any patient has ongoing toxicities at this time, the data will continue to be collected in the patient's notes and any SAEs reported to AstraZeneca Patient Safety in accordance with Section 5.10.4. Additionally as stated in Section 5.10.3 (Handling unresolved adverse events/serious adverse events at withdrawal), any SAE or non-serious adverse event, that is ongoing at the end of the study, must be followed up to resolution or stabilization of the toxicity or until the patient starts another anticancer therapy or unless in the opinion of the investigator the condition is unlikely to resolve due to the patients underlying disease.

### **6.6.1 Patient Management Post Data cut-off**

#### **6.6.1.1 Patients continuing on AZD2281**

[figure not shown]
There will be a final data cut-off defined as the time when all patients receiving AZD2281 have been followed for a minimum of 3 months of monotherapy AZD2281 following combination treatment, or there are no more patients remaining on treatment in the study; whichever is the earlier date. At this time point, the clinical study database will close to new data. Patients are however permitted to continue to receive study treatment beyond the closure of the database if, in the opinion of the investigator, they are continuing to receive benefit from treatment with AZD2281. Patients continuing on study treatment will be followed for core safety assessments only (haematology, clinical chemistry, AEs/SAEs and concomitant medications, IMP dosing details).

For patients who do continue to receive treatment beyond the time of this data cut-off, investigators will continue to report all SAEs to AstraZeneca Patient Safety until 30 days after study treatment is discontinued, in accordance with Section 5.10.4 (Reporting of Serious Adverse Events). Additionally as stated in Section 5.10.3 (Recording of adverse events), any SAE or non-serious adverse event that is ongoing at the time of this data cut-off, must be followed up to resolution unless the event is considered by the investigator to be unlikely to resolve, or the patient is lost to follow-up.

Patients continuing on monotherapy AZD2281 at the data cut-off should attend visits according to routine clinical practice but at least every 8 weeks until they meet any discontinuation criteria as per Section 4.4.6.1.

Drug accountability should continue to be performed until the patient stops study treatment completely.

**Figure 4** Flowchart to describe how to handle patients after the data cut-off date

\* Core safety assessments - haematology, clinical chemistry, AEs, concomitant medications

## 6.7 Data Management

Data management will be performed by AstraZeneca Data Management Centre staff.

When the completed paper Case Report Forms have been scanned and indexed, the data are entered into the study database and proofread.

The data collected through third party sources will be obtained and reconciled against study data.

Adverse events and medical/surgical history will be classified according to the terminology of the latest version the Medical Dictionary for Regulatory Activities (MedDRA). Medications will be classified according to the AstraZeneca Drug Dictionary. All coding will be performed by the Medical Coding Team at the AstraZeneca Data Management Centre.

Data queries will be raised for inconsistent, impossible or missing data. All entries to the study database will be available in an audit trail.

The data will be validated as defined in the Data Management Plan. Quality control procedures will be applied to each stage of data handling to ensure that all data are reliable and have been processed correctly.

When all data have been coded, validated, signed and locked, clean file will be declared. Any treatment revealing data may thereafter be added and the final database will be locked.

Data associated with biological samples will be transferred to laboratories internal or external to AstraZeneca.

#### **6.7.1 Case report forms**

Paper CRFs (pCRFs) will be used to record all data not captured electronically. Data should be recorded legibly onto the pCRFs in blue or black ballpoint pen. Correction fluid or covering labels must not be used.

The AstraZeneca Monitor will check data at the monitoring visits to the study site. The Investigator will ensure that the data in the pCRFs are accurate, complete and legible.

Data from the completed pCRFs will be entered onto AstraZeneca's clinical study database and validated under the direction of the Data Manager. Any missing, impossible or inconsistent recordings in the pCRFs will be referred back to the Investigator using a data query form and be documented for each individual patient before clean file status is declared.

#### **6.7.2 Genetic data**

In the case of genotypic data, only the date the patient gave consent to participation in the genetic research and the date the blood sample was taken from the patient will be recorded in the CRF and database.

The genotypic data generated from the study will be stored in the AstraZeneca LIMS database or other appropriate system. This database is a secure database, which is separate from the database used for the main study. Some or all of the datasets from the main clinical study dataset may be duplicated within the AstraZeneca LIMS database or other appropriate system for exploratory analysis.

## **6.8 (PGx) Reporting of genotypic results**

Results from any genetic research performed will be reported separately from the clinical study report. AstraZeneca will not provide individual genotype results to patients, their family members, any insurance company, an employer, clinical study investigator, general physician or any other third party, unless required to do so by law. The patient's DNA will not be used for any purpose other than those described in the study protocol.

Individual patients will not be identified in any report or publication resulting from this work. The data and results of this study may be reviewed with collaborators and published, but neither the patient's name nor any other personal identifiers will appear in any publication or report.

## **7. PHARMACOKINETIC, SAFETY, GENETIC AND STATISTICAL METHODOLOGY**

### **7.1 Pharmacokinetic evaluation**

#### **7.1.1 Calculation or derivation of pharmacokinetic variables**

The pharmacokinetic analyses will be performed by [REDACTED]

All plasma concentration-time data will be analysed using non-compartmental methods by WinNonlin Version 4.1 Enterprise.

$C_{max}$ ,  $t_{max}$  and  $AUC_{0-t}$  for AZD2281 will be calculated for each patient directly from their plasma concentration-time profiles, and  $AUC_{0-t}$  will be calculated by the linear trapezoidal rule.

### **7.2 Efficacy evaluation**

#### **7.2.1 Calculation or derivation of efficacy variables**

ORR is defined as the percentage of patients who have at least one RECIST assessment response of CR or PR. Data obtained up until progression, or last evaluable assessment in the absence of progression will be included in the assessment of ORR. The ORR will be based on the investigator visit assessment of RECIST response and will not be derived programmatically by AZ. Depending on the number of patients with non-measurable disease, ORR may also be calculated for the subset of patients with measurable disease only

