#### 4.4.2 Inclusion criteria

For inclusion in the study patients must fulfil all of the following criteria:

1. Fully-informed written consent.
2. Adequate bone marrow, hepatic and renal function including the following:
  - Haemoglobin  $\geq 9.0$  g/dL
  - White blood cell count (WBC)  $> 3 \times 10^9/L$
  - Absolute neutrophil count (ANC)  $\geq 1.5 \times 10^9/L$
  - Platelet count  $\geq 100 \times 10^9/L$ ;
  - Total bilirubin  $\leq 1.5$  x institutional upper limit of normal (ULN);
  - AST (SGOT), ALT (SGPT)  $\leq 2.5$  x institutional upper limit of normal unless liver metastases are present in which case it must be  $\leq 5$ x ULN
  - Serum creatinine  $\leq 1.5$  mg/dL x institutional upper limit of normal (ULN)
  - Creatinine Clearance  $> 50$  mL/min (calculated or 24 hour urine sample)
3. Male or female patients, age  $\geq 18$  years
4. Performance status (PS)  $\leq 2$  (ECOG scale) (see [Appendix F](#))
5. The patient is willing and able to comply with the protocol for the duration of the study, including hospital visits for treatment and scheduled follow-up visits and examinations.
6. Negative pregnancy test for women of childbearing potential only.
7. Histologically confirmed metastatic cancer, not amenable to surgery or radiation therapy with curative intent for whom no standard (or approved) therapy is available.
8. Life expectancy of at least 12 weeks.
9. Patients with measurable or non measurable disease according to RECIST (see [Appendix D](#))

For inclusion in the genetic component of the study, patients must fulfil the following criterion:

- Provision of informed consent for genetic research

If a patient declines to participate in the pharmacogenetic component of the study, there will be no penalty or loss of benefit to the patient. The patient will not be excluded from other aspects of the study described in this Clinical Study Protocol, so long as they consent.

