## **5.2 Assessment of Anti-Neoplastic activity**

Only tumour assessments according to RECIST ([Appendix D](#)) should be performed at baseline (within 28 days before first dose) and according to the planned study assessments (Section 4.2). Scans that were performed as part of standard of care prior to signature of the informed consent form can be analysed for the purposes of the study if they were performed within the correct time frame and of sufficient quality. It is important to follow the assessment schedule as closely as possible.

Baseline contrast-enhanced CT of the chest, abdomen and pelvis should be performed for the assessment of measurable lesions. Where iodine contrast is contraindicated then contrast-enhanced MRI of the abdomen and pelvis is preferred. Other regions should be scanned at baseline and followed up where clinically indicated for the assessment of disease. Lesions must be assessed using the same method and technique on each occasion.

Unequivocal malignant disease not identified prior to starting study treatment on additional anatomical imaging (e.g. computed tomography (CT), magnetic resonance imaging (MRI) or bone scan confirmed by X-ray), prompted by symptoms is considered disease progression and should be recorded as new lesions.

Categorisation of the objective tumour response assessments will be based on the RECIST criteria for target and non-target lesions ([Appendix D](#)). Response will be calculated in comparison to the baseline tumour measurements obtained before starting treatment. Progression will be calculated in comparison to when the tumour burden was at a minimum (ie, smallest sum of longest diameter previously recorded since starting treatment)

Patients with non-measurable disease only are not excluded from this study. These patients should be followed up with the same assessment schedule as those with measurable disease at baseline, preferably using contrast enhanced CT or MRI where CT is not feasible (see [Appendix D](#) for methods). Patients with non-measurable disease only will be assessed according to RECIST criteria for non-target and new lesions (see [Appendix D](#)).

Lesion details will be recorded on the CRF page in the same order as they were recorded at screening. Details of any new lesions will also be collected.

Note: Patients will be assessed according to RECIST version 1.0

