#### **7.4.4 Methods of statistical analyses**

No formal statistical analyses will be performed on safety data (primary objective), PK data, and efficacy data. All data will be summarised descriptively and where appropriate, confidence intervals will be presented as measures of study precision

Categorisation of response rate will be based on the RECIST criteria ([Therasse et al 2000](#)) using the following response categories: complete response (CR), partial response (PR), stable disease (SD) and progressive disease (PD). A patient will be classified as a responder if the RECIST criteria for a CR or PR are satisfied at any time up to and including the defined analysis cut-off point. ORR is the number of CR and PR divided by the number of enrolled patients evaluable for RECIST.

ORR will be analysed in the same way as described for the primary analysis. ORR and best overall objective response categories will be summarised at each assessment and overall by allocated study treatment. Conformed responses will be summarised where possible. The proportion of patients with responses will be presented along with corresponding 95% confidence intervals using the Wilson score method ([Newcombe 1998](#)).

Safety, tolerability and PK data will be summarised descriptively and with plots, further details of which will be provided in the SAP.

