**Table 2 Overall Visit Response for Target Lesions**

Complete Response (CR)	Disappearance of all target lesions since baseline
Partial Response (PR)	At least a 30% decrease in the sum of the LD of target lesions, taking as reference the baseline sum LD
Stable Disease (SD)	Neither sufficient shrinkage to qualify for PR nor sufficient increase to qualify for PD
Progressive Disease (PD)	At least a 20% increase in the sum of the LD of target lesions, taking as reference the smallest sum LD recorded since the treatment started
Not Evaluable (NE)	Only relevant if any of the target lesions were not assessed or not evaluable or had a lesion intervention
Not applicable (NA)	Only relevant if there are no target lesions at baseline

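### Under Appendix D Table 4, patients with only non-measurable disease cannot be scored as responders, yet the ORR denominator appears to include them and the measurable-disease ORR is only optional

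*Protocol*

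**What the plan says.** **Eligibility.** Section 4.4.2 admits "Patients with measurable or non measurable disease according to RECIST", and Section 5.2 repeats the point: "Patients with non-measurable disease only are not excluded from this study". No cap is set.

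**Follow-up.** These patients have the same assessment schedule as the others. Section 5.2 says: "Patients with non-measurable disease only will be assessed according to RECIST criteria for non-target and new lesions".

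**ORR.** Section 7.2.1: "ORR is defined as the percentage of patients who have at least one RECIST assessment response of CR or PR". Section 7.4.4: "ORR is the number of CR and PR divided by the number of enrolled patients evaluable for RECIST". The protocol does not define evaluability for RECIST. An ORR confined to measurable disease appears once, in Section 7.2.1, as a possible addition: "Depending on the number of patients with non-measurable disease, ORR may also be calculated for the subset of patients with measurable disease only". Section 7.4.4 asks for ORR overall and by allocated treatment, with 95% Wilson intervals.

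**Scoring.** In Appendix D Table 2, a target-lesion response of NA is "Only relevant if there are no target lesions at baseline". In Appendix D Table 4, target NA with a non-target response of either CR or IR/SD and no new lesion gives an overall response of SD. The other NA rows give NE or PD.

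**Who scores.** Section 7.2.1: "The ORR will be based on the investigator visit assessment of RECIST response and will not be derived programmatically by AZ". Appendix D Section 4.6, in contrast, has the sponsor derive overall visit response and best overall response from the lesion data during the analysis.

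**The concern.** A response rate is readable only if each patient in the denominator could in principle reach the numerator. Here one eligible group seems to be counted below the line while the scoring table gives it no route to CR or PR. Two consequences follow.

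- The overall ORR is pulled down by the share of such patients, whatever the activity of the combination.
- ORR by dose is compared across very small cohorts (3–6 patients on continuous dosing, 12 or 4–12 on intermittent dosing). A few more non-measurable patients in one cohort than in another can look like a difference in activity.

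The figure that would show this, ORR in measurable disease, is optional and has no threshold. The study is open label, so a decision about whether to show it can be taken by people who already know the responses.

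**Working it through.** The protocol states no target ORR, no expected ORR and no expected share of non-measurable patients, so there is no planned figure to reproduce. The check has a logical part and an illustrative part.

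**1. Can a patient without target lesions be scored CR or PR under Appendix D Table 4?**

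| Target | Non-target | New lesion | Overall |
|---|---|---|---|
| NA | CR or IR/SD | No | SD |
| NA | NE | No | NE |
| NA | PD | Yes or No | PD |
| Any | Any | Yes | PD |

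None of these rows gives CR or PR.

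**2. Is the row consistent with the rest of the appendix?** Appendix D Table 3 defines a non-target CR as the disappearance of all non-target lesions. Table 4 treats the mirror case as neutral: target CR with non-target NA gives overall CR. But target NA with non-target CR gives SD. Complete disappearance of all recorded disease is therefore CR for one patient and SD for another, according to lesion type alone.

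**3. Are these patients in the denominator?** Section 7.4.4 limits it to RECIST-evaluable patients and does not mention measurability. Section 5.2 has non-measurable-only patients assessed under RECIST. Section 7.2.1 calls the measurable-disease ORR an additional calculation in a subset, which makes sense only if the main ORR covers more than that subset.

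**4. Size.** Let f be the share with only non-measurable disease, p the ORR in measurable disease and q the recorded response rate in non-measurable-only patients. Then

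reported ORR = (1 − f) × p + f × q.

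Under Table 4, q = 0, so reported ORR = (1 − f) × p, and it cannot exceed 1 − f.

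With p = 40% (assumed) and f from 10% to 40% (assumed):

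- f = 10%: 0.90 × 40% = 36%
- f = 25%: 0.75 × 40% = 30%
- f = 40%: 0.60 × 40% = 24%

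**5. Intervals at the planned enrolment of 60**, with f = 25% and p = 40%. Non-measurable-only: 0.25 × 60 = 15. Measurable: 45. Responders: 0.40 × 45 = 18. The Wilson 95% limits are

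[x/n + z²/(2n) ± z√(p̂(1 − p̂)/n + z²/(4n²))] / (1 + z²/n), with p̂ = x/n and z = 1.96.

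- All evaluable: 18/60 = 30.0% (19.9 to 42.5)
- Measurable only: 18/45 = 40.0% (27.0 to 54.5)

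**6. Cohort level (case mix assumed).**

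- 12 patients, 4 of them non-measurable-only, 3 responders: 3/12 = 25.0% (8.9 to 53.2) against 3/8 = 37.5% (13.7 to 69.4).
- 6 patients, 3 of them non-measurable-only: the highest attainable ORR is 3/6 = 50%.

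**The case against.** Several objections have force, and they limit how far the point goes.

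- **A reader might infer that these patients can never be responders.** The documents do not support that without a condition. Section 7.2.1 rests ORR on the investigator's visit assessment, and Appendix D Table 3 offers a non-target CR category, so an investigator who departs from Table 4 could record a CR. Appendix D is, however, written for investigator assessment, so Table 4 is the rule they would be expected to follow. The zero holds if Table 4 is applied.
- **A reader might infer that the protocol expressly puts these patients in the denominator.** It does not. Evaluability is undefined, and the analysis plan could define it. Their inclusion is the natural reading of three sections taken together.
- **A reader might infer that the subset analysis is triggered by the responses.** The trigger named is the number of patients with non-measurable disease, which is a baseline count. What stands is that no threshold is fixed and the analysis remains optional in an open-label study.
- **The modification is deliberate.** Appendix D Section 1 adapts RECIST to admit both kinds of disease, and response among all evaluable patients is a legitimate descriptive quantity. That supports keeping it as a second figure. It does not explain why disappearance of all non-target disease is scored SD.
- **The consequences are modest.** ORR supports a preliminary assessment of activity, no formal analysis is planned, and escalation rests on DLT and safety review. In the 60-patient illustration the two intervals overlap widely.

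**Conclusion.** The point holds in a conditional form. If Table 4 is applied and non-measurable-only patients count as evaluable, the reported ORR is (1 − f) times the measurable-disease ORR. This is a relative understatement of f, and cohort figures move with chance case mix.

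The actual size is unknown: f, the 40% ORR and the cohort mixes are all assumptions, and if few such patients enrol the effect is close to nil. Some are likely, because Appendix D Section 2 classes bone lesions, effusions and previously irradiated lesions as non-measurable and the population has metastatic disease.

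This goes beyond detail left to the analysis plan. The protocol itself states the denominator, the scoring rows and the optional status of the corrective analysis, and it disagrees with itself on who determines response. It is worth correcting, but in proportion: no error rate, sample size or escalation decision depends on it.

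**What to change.** 1. **Sections 7.2.1 and 7.4.4.** Remove the conditional sentence on the measurable subset. State that the main ORR is CR plus PR among RECIST-evaluable patients with measurable disease at baseline, always reported. Keep the existing evaluability criterion, so that the handling of unevaluable patients does not change unnoticed, and define it. Report the all-evaluable ORR as supportive, and show the number of non-measurable-only patients in each cohort.
2. **Appendix D Table 4.** Reconcile the NA row with Table 3 by splitting it: non-target CR with no new lesion is scored CR, and IR/SD is scored SD. Once the first change is made, this affects only the supportive ORR.
3. **Section 7.2.1 and Appendix D Section 4.6.** Settle whether ORR uses the investigator's visit response or the sponsor's derivation, and say so in both places.

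**Cost.** No new data are needed. The main interval widens somewhat: in the 60-patient illustration from 22.6 percentage points (42.5 − 19.9) to 27.5 (54.5 − 27.0). As the protocol has already reached Amendment 6, splitting the NA row may mean re-scoring visits already recorded for patients without target lesions, so the second change may involve more than wording.

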### **7.3 Safety evaluation**

#### **7.3.1 Calculation or derivation of safety variables – Not Applicable**

#### **7.3.2 Other significant adverse events (OAE)**

During the evaluation of the AE data, an AstraZeneca medically qualified expert will review the list of AEs that were not reported as SAEs and DAEs. Based on the expert's judgement,

significant adverse events of particular clinical importance may, after consultation with the Global Patient Safety Physician, be considered OAEs and reported as such in the Clinical Study Report. A similar review of laboratory/vital signs data will be performed for identification of OAEs.

Examples of these may be marked haematological and other laboratory abnormalities, and certain events that lead to intervention (other than those already classified as serious), dose reduction or significant additional treatment.

